1 BACKGROUND

Mpox (or MPX) (previously known as Monkeypox) is an acute febrile rash illness caused by the mpox virus, an orthopox virus related to variola virus (causative agent of smallpox), cowpox virus and the vaccine strain vaccinia virus.

Since the first identification of a mpox infection in humans in 1970, the majority of human cases have been reported from Africa, including sporadic outbreaks that usually resulted from contact with wildlife reservoirs, in particular rodents. Animal-to-human (zoonotic) transmission can result from direct contact with the blood, bodily fluids, or cutaneous or mucosal lesions of infected animals. There are two distinct genetic clades of the mpox virus: the central African or Congo Basin clade (Clade 1) and the west African clade (Clade 2). The case fatality ratio of mpox has historically ranged from 0 to 11 % in the general population and has been higher among young children. In recent times, the case fatality ratio has been around 3–6%. The central African (Congo Basin) clade has historically caused more disease and was thought to be more transmissible. (WHO fact sheet) Human-to-human transmission can result from close contact with respiratory secretions, skin lesions of an infected person or recently contaminated objects. Transmission via droplet respiratory particles usually requires prolonged face-to-face contact. (WHO fact sheet) Cross-immunity exists between different orthopox viruses, and, in the past, vaccination against smallpox was protective against mpox infection. However, the global smallpox vaccination campaigns were discontinued after eradication of the disease, likely leaving the population below 40 to 50 years of age (depending on the country) more susceptible to mpox.

Mpox is usually a self-limited disease with the symptoms lasting from 2 to 4 weeks. Severe cases occur more commonly among children and are related to the extent of virus exposure, patient health status and nature of complications. Underlying immune deficiencies may lead to worse outcomes. Complications of mpox can include secondary infections, bronchopneumonia, sepsis, encephalitis, and infection of the cornea with ensuing loss of vision.

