4 STUDY DESIGN

This is an observational retrospective cohort study.

In total, approximately 2000 cases from PLHIV and PrEP users will be analysed

Only real-world retrospective, routine data will be used for this study. Deidentified data will be transcribed into the Electronic Case Report Form (eCRF) system from source data at each clinical site or from existing cohort databases, where appropriate.

Case data will be collected until the Date of clinical resolution e.g. lesion resolution, hospital discharge or death (up to 3 months)

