5.1 Inclusion Criteria

- Diagnosis of MPX was more than 90 days prior to data collection
- Confirmed MPX infection by documented PCR testing on skin and/or mucosal and/or any anatomical site between 1st May 2022 to 1st December 2023
- At least 18 years of age
- Cases (PLWHIV + MPX)
 - Documented HIV-1 infection
- Cases (PrEP users + MPX)
 - Attended a clinic to receive PrEP or self-procured PrEP at time of Mpox diagnosis.

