6 STUDY PROCEDURES

6.1 Participant Identification

Most People living with HIV (PLWHIV) and HIV negative PrEP users will be identified from sites in the NEAT ID network. PLWHIV are routinely followed-up at specialised outpatient clinics with regular follow up visits as standard of care and many of these centres take care of patients on PrEP. Patients are taking PrEP to prevent contraction of HIV as they perceive themselves to be at risk due to frequent sexual activity with different partners.

In July 2022, NEAT ID opened a dashboard to 150 sites from 20 countries to provide basic information about the number of PLWHIV with MPX and disease outcomes at their centres (<https://www.NEAT-ID.org/>). Data were provided from patients' cases from April 2022 until November 2022 from 31 global sites, 26 sites from 16 European countries and 5 site in Latin America. The dashboard provided a first estimate about the total numbers of PLWHIV with MPX and where these patients are in continued care. As of the end of November 2022, 907 PLWHIV with MPX were reported in care, with 53 hospitalisations and 1 death from an estimated number of 85,279 PLWHIV in routine care at these sites ([name] *et al*, EACS 2023). These case numbers strongly suggested feasibility to recruit sufficient numbers of PLWHIV with MPX and that patients have been identified at their centres already.

A feasibility study of patients receiving PrEP across the NEAT ID network have identified 45 sites that provide PrEP services for a total of 27,416 PrEP users with 1,361 new PrEP initiators each month.

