6.2 Data collection

Only real-world retrospective data will be used for this study. Patients who have had mpox and fulfil the entry criteria will be enrolled after 90 days from date of diagnosis to allow for follow up data to be collected. Pseudonymised retrospective data will be transcribed into the eCRF system from source data at each clinical site or from existing cohort databases, where appropriate. No personal identifiable data will be transmitted to NEAT ID. The data elements will be transcribed from source data according to the data collection list below. Mechanisms to ensure data quality and integrity will be deployed as per applicable standard operating procedures and in line with Good Documentation Practice (GDocP) and Good Pharmacoepidemiology Practice (GPP). Patients will be identified and documented by participating sites.

For all patients with MPX the following information will be collected where routinely available:

- Age (year of birth)
- Sex and gender identity
- Ethnicity (where available)
- HIV status
- HIV pre-exposure prophylaxis (PrEP) use
- Comorbidities and Medical history (diabetes mellitus, other immunosuppression (e.g. solid organ transplant), known chronic kidney or liver disease, mental health conditions)
- Recent sexual history (3 months) – number of recent partners
- Recent and/or concomitant sexually transmitted infections
- Orthopoxvirus vaccination history (if available)
- Symptom onset date (fever onset, lesion onset, rectal pain)

- Date of positive PCR test result (documented)
- MPX severity -Reported clinical signs and symptoms of mpox (e.g. rash, mouth lesions, rectal pain, breathlessness)
- Time to resolution of lesions, if known
- Mortality as a consequence of MPX including cause
- Hospitalisation for MPX and length of hospitalisation
- Drug treatment for MPX (Tecovirimat, other)
- Drug for complications associated with MPX (laxatives, antibiotics, analgesia)
- recent travel to/living in endemic country or country with outbreak
- contact with suspected, probable, or confirmed case (if known)
- contact with infected animal (if known)

For PLWHIV the following additional information will be collected:

- Date of HIV diagnosis
- Current Antiretroviral Therapy/Treatment (ART)
- If not on ART, reason for not being on ART
- Last CD4 cell count (including CD4% and CD4/CD8 ratio) and
- Last HIV-RNA before MPX diagnosis

Skin lesion at peak severity score:

- Not presenting with skin lesions (0 skin lesions)

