7.4 Primary outcome analysis

The first primary outcome analysis will be to describe outcomes of MPX in PLWHIV and in PrEP users in terms of severity of lesions, time to lesion resolution, hospitalization, death.

The rate of serious lesions will be estimated by dividing the number of participants with serious lesions by the total number of participants in the full analysis population. Unadjusted and adjusted odds ratios (ORs) will be calculated using the logistic regression model to assess the impact of HIV on the occurrence of serious lesions compared to PrEP users.

Because some participants' lesion may not be healed by the end of the study period and, therefore, the duration of resolution would not be known, and thus right-censored, survival analysis methods such as the Kaplan-Meier and Cox model will be used to assess the time to lesion resolution. Kaplan-Meier estimates will be used to estimate the median time to lesion resolution. Unadjusted and adjusted hazard ratios (HR) will be estimated using the Cox proportional hazard model to assess the impact of HIV-infection on the time to lesion resolution compared with PrEP users.

The hospitalization rate will be estimated by dividing the number of participants hospitalized for mpox infection by the total number of participants in the total analysis population. Unadjusted and adjusted odds ratios (ORs) will be calculated using the logistic regression model to compare hospitalization rates between PLWHIV and PrEP users.

The mortality rate will be estimated using the Kaplan-Meier Method. Unadjusted and adjusted hazard ratios (HR) will be calculated using the Cox proportional hazard model to compare the rates of mortality between PLWHIV and PrEP users.

Adjustment variables will include the following potential confounders: Age (<30 vs 30-40 vs >40 years); Sex at birth (female vs male); Comorbidities; multiple sexual partners (yes vs no); number of sexual partners in the last 3 months prior to mpox diagnosis; and smallpox vaccination history (yes vs no).

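### Mortality is to be estimated by Kaplan-Meier with no censoring rule while case data stop at recovery; used as collected, those data would overstate case fatality when a death is late

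*Combined protocol and SAP*

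**What the plan says.** Death is one of the primary outcomes (section 3.3). For it, section 7.4 states: "The mortality rate will be estimated using the Kaplan-Meier Method". Hazard ratios from a Cox model then compare PLWHIV with PrEP users. No time origin, horizon or censoring rule is given for this analysis.

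Section 4 fixes when data on a case end: "Case data will be collected until the Date of clinical resolution e.g. lesion resolution, hospital discharge or death (up to 3 months". The synopsis has the same rule.

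Three other places bear on the point:

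- Section 5.1 requires: "Diagnosis of MPX was more than 90 days prior to data collection". Section 6.2 repeats the 90-day interval.
- The data list in section 6.2 includes "Mortality as a consequence of MPX including cause", but no item for vital status at a fixed day.
- Section 7.4 estimates serious lesions and hospitalisation as simple proportions of the analysis population. Section 7.5 uses competing-risk methods, but only for length of stay.

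**The concern.** Kaplan-Meier assumes that a censored patient has the same future risk of the event as those still under observation. If data end at recovery and nothing else is specified, the patients censored are those who have recovered, and those left at risk are the ones still ill. The event is death from mpox, so the two groups do not share a risk. More deaths would not remove this problem.

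The resulting percentage would answer what mortality would be if nobody recovered. Readers would take it for case fatality. Few deaths are likely, so a single late one could set the published figure for a primary outcome. The group comparison is affected too. A Cox model on the same data compares the hazard of death among patients not yet resolved. That is not the risk of death after diagnosis if one group heals more slowly.

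**Working it through.** The plan gives no mortality, event-count or power figure for death, so there is nothing of its own to reproduce.

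**Inputs from the documents**

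- Healing time (section 1): "Mpox is usually a self-limited disease with the symptoms lasting from 2 to 4 weeks".
- Earlier death count (section 6.1): "907 PLWHIV with MPX were reported in care, with 53 hospitalisations and 1 death". This is 1/907 = 0.11%, exact 95% CI 0.003% to 0.61%.
- Size (section 4): "In total, approximately 2000 cases from PLHIV and PrEP users will be analysed". No split by group is stated. If the 1/907 rate applied to all cases, about 1.1 deaths would be expected in 1,000 (1,000/907) and 2.2 in 2,000 (2,000/907).

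**Assumption.** Time to resolution is lognormal. The documents give only the 2 to 4 weeks, so the spread is varied. With the median at √(14 × 28) = 19.8 days, the share resolving between days 14 and 28 is set at 95%, 80% or 50%.

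**Formulas, for one death on day t among N cases**

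- Kaplan-Meier, recovered patients censored at resolution: 1/n(t), where n(t) is the number still unresolved on day t, including the patient who dies.
- Recovered patients carried alive to day 90: 1/N.
- Cumulative incidence (Aalen-Johansen) with resolution as a competing event: [n(t)/N] × [1/n(t)] = 1/N.

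The last two equal the crude proportion whatever the day of death. With N = 907 both give 0.11%.

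**Kaplan-Meier mortality, N = 907, one death** (number at risk; ratio to 0.11%)

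| Day of death | 95% in days 14-28 | 80% | 50% |
|---|---|---|---|
| 7 | 0.11% (907; 1.0) | 0.11% (907; 1.0) | 0.11% (888; 1.0) |
| 14 | 0.11% (884; 1.0) | 0.12% (816; 1.1) | 0.15% (680; 1.3) |
| 21 | 0.30% (336; 2.7) | 0.27% (376; 2.4) | 0.24% (413; 2.2) |
| 28 | 4.2% (24; 38) | 1.1% (92; 9.9) | 0.44% (227; 4.0) |
| 35 | 50% (2; 454) | 5.9% (17; 53) | 0.82% (122; 7.4) |
| 42 | 100% (1; 907) | 33% (3; 302) | 1.5% (66; 14) |

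**Second set of assumptions.** N = 1,000, median 21 days, n(t) = 1,000 × [1 − Φ(ln(t/21)/s)], true value 0.1%. With s = 0.35 about 67% resolve between days 14 and 28; with s = 0.5 about 51% do.

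- Day 28: 206 (s = 0.35) or 283 (s = 0.5) at risk, giving 0.49% or 0.35%.
- Day 35: 72 or 154 at risk, giving 1.4% or 0.65%.
- Day 42: 24 or 83 at risk, giving 4.2% or 1.2%, which is 42 or 12 fold.

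Slower healing reduces the inflation. With a median of 24 days and s = 0.5, 132 remain at day 42, giving 0.76%, or 7.6 fold.

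**The case against.** The strongest reply is that censoring at recovery is nowhere written. Section 4 says when data collection stops; it is not an analysis rule. Section 6.2 says "Patients who have had mpox and fulfil the entry criteria will be enrolled after 90 days from date of diagnosis" so that follow-up can be captured, and it lists mpox death as an item without a cut-off at resolution. An analyst could censor everyone without an mpox death at day 90, and Kaplan-Meier would then equal the crude proportion. This stands as far as certainty goes: the bias is conditional. It does not clear the plan, because no section carries recovered patients alive to 3 months or treats resolution as a competing event. The data rule as written points to censoring at recovery.

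A reader might infer that mortality will be inflated by an order of magnitude. The documents do not support that. They do not say when deaths occur, and a death in the first two weeks gives almost no inflation.

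A reader might also infer that slower-healing PLWHIV will look protected. One death per group on day 42, with median healing of 24 against 21 days (s = 0.5), gives 0.76% (1/132) against 1.21% (1/83). But that rests on one death per group, a chosen day and an assumed 3-day difference, and one death against one cannot separate groups under any estimator. Nor is the Cox ratio plainly biased. It is a cause-specific hazard ratio among unresolved patients, a recognised quantity that does not compare risk of death.

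Finally, the study is mainly descriptive and a reported death count would expose an inflated curve. That limits the harm, but death remains a primary outcome with a prescribed estimator. Lesion severity and hospitalisation are unaffected.

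**Conclusion.** The concern holds in conditional form. Sections 4 and 7.4 together leave the mortality censoring rule open. If the data are analysed as collected, recovered patients are censored informatively and the Kaplan-Meier percentage overstates case fatality.

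For one death in about 900 to 1,000 cases and median healing of 20 to 21 days, the overstatement runs from almost none by day 14 to at least 12 fold at day 42; at day 28 it spans about 4 to 38 fold. These ranges rest on lognormal healing and an assumed spread, and they shrink if healing is slower. The direction does not depend on those assumptions, provided recovered patients have little remaining risk of mpox death. The Cox ratio needs a different interpretation from the one the plan gives it.

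**What to change.** In section 7.4, replace Kaplan-Meier mortality with the proportion who died of mpox within 90 days of diagnosis, by group, with death counts and exact 95% confidence intervals. Use the full analysis population, as for hospitalisation.

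- Count patients with documented resolution as alive for mpox death.
- Report separately those with neither documented resolution nor known vital status, and add a best-case and worst-case sensitivity analysis for them.
- If a time-to-death display is kept, use a cumulative incidence with resolution as a competing event. This needs no new data.
- If the Cox ratio is kept, label it as a cause-specific hazard ratio among unresolved patients.
- Record day-90 vital status where the existing record holds it. This is desirable but not essential: section 5.1 guarantees that 90 days have passed, not that status is on file, and users who procured PrEP themselves may not have re-attended.

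The cost is a small wording change to the protocol and the loss or redefinition of the Kaplan-Meier mortality curve. The worst-case bound may be wide if many patients have unknown status.

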The second primary outcome analysis will be performed between PLWHIV with MPX versus PrEP users with MPX. The endpoint is to assess differences in clinical manifestations of MPX between the groups. Unadjusted and adjusted odds ratios (ORs) will be calculated using the logistic regression models to compare the rates of clinical manifestations between PLWHIH and PrEP users. The adjusted variables will be the following (potential confounders): Age (<30 vs 30-40 vs >40 years); Sex at birth (female vs male); Comorbidities; multiple sexual partners (yes vs no); number of sexual partners in the last 3 months prior to MPX diagnosis; and smallpox vaccination history (yes vs no).

The third primary outcome analysis will be performed within the PLWHIV group. The endpoint is to evaluate the characteristics of HIV infection associated with severe mpox. Univariable and multivariable logistic regression models will be used to assess factors associated with severe mpox in PLWHIV. The following variables will be evaluated: time since HIV diagnosis (years); current ART; CDC disease stage; CD4 cell nadir; last CD4 cell count/HIV-RNA before MPX diagnosis (including CD4% and CD4/CD8 ratio). Variables achieving $P < 0.20$ in the univariable analysis will be retained for the multivariable analysis.

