7.5 Secondary outcome analysis

All secondary outcome analysis will be performed on PLWHIV with MPX compared to PrEP users with MPX.

The prevalence of MPX per site during the study period will be estimated by the number of MPX patients attending the site divided by the total number of patients the sites saw during the study period. The 95%

Confidence Interval of the prevalence will be calculated with the exact Clopper-Pearson method. Fisher exact test will be used to compare the prevalence of MPX in HIV-infected individuals to that of PrEP users.

The length of stay in hospital will be estimated using competing risk models with death as a competing event. Gray's test will be used to compare the duration of hospitalisation between PLWHIV and PrEP users. Unadjusted and adjusted sub-distribution hazard ratios (sHR) will be calculated using competing risk models with death as a competing event. The duration of hospitalization will be defined by the time (days) from hospitalization to hospital discharge or last observation. Adjustment variables will include: Age (<30 vs 30-40 vs >40 years); Sex at birth (female vs male); Comorbidities; multiple sexual partners (yes vs no); number of sexual partners in the last 3 months prior to mpox diagnosis; and Orthopoxvirus vaccination history (yes vs no).

Subgroup analyses for clinical manifestation in MPX will be conducted to assess the difference between PLWHIV and PrEP users across comorbidities. The following comorbidities will be assessed: diabetes mellitus, immunosuppression (e.g. solid organ transplant), chronic kidney or liver disease, mental health illness. Adjusted odds ratio will be calculated to compare PLWHIV and PrEP users within subgroup using logistic regression models. Adjustment variables will include: Age (<30 vs 30-40 vs >40 years); Sex at birth (female vs male); multiple sexual partners (yes vs no); number of sexual partners in the last 3 months prior to mpox diagnosis; and smallpox vaccination history (yes vs no).

Heterogeneity in the impact of HIV infection on clinical manifestations based on comorbidities will be assessed by including terms for interactions between patient status (PLWH and PrEP users) and the comorbidity variable in multivariable logistic regression models. All variables described above for adjustments will be included in the multivariable models.

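### Age enters the adjusted PLWHIV-versus-PrEP models only as three bands, although year of birth is collected; this can leave residual age confounding, mainly in the open-ended over-40 band

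*Combined protocol and SAP*

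**What the plan says.** - Section 7.4, first primary analysis (serious lesions, time to lesion resolution, hospitalisation, death): the age term is "Age (<30 vs 30-40 vs >40 years", within the list "Adjustment variables will include the following potential confounders: Age (<30 vs 30-40 vs >40 years); Sex at birth (female vs male); Comorbidities; multiple sexual partners", followed by number of partners and smallpox vaccination.
- Section 7.4, second primary analysis (clinical manifestations) repeats the coding: "The adjusted variables will be the following (potential confounders): Age (<30 vs 30-40 vs >40 years".
- Section 7.5 uses the same three bands for length of stay and for the comorbidity subgroup and interaction models: "Adjustment variables will include: Age (<30 vs 30-40 vs >40 years); Sex at birth (female vs male".
- Section 6.2 collects "Age (year of birth", which gives age to within about a year. Section 5.1 requires "At least 18 years of age" and sets no upper limit, so the top band is open-ended.
- No reason is given for the cut points. No continuous, spline or finer-band age term is planned. The only sensitivity analysis, in section 7.7, is complete-case and does not touch age coding.

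**The concern.** Banding a continuous confounder removes its effect between bands but not within them. The over-40 band covers everyone from 41 upwards. If PLWHIV in that band are on average older than PrEP users in it, the model treats them as the same age and credits any remaining age effect to HIV.

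The study's first central question (section 2) is whether PLWHIV have a more severe course than PrEP users. If PLWHIV are older and risk rises with age, the leftover confounding points the same way as the hypothesis in section 3. If risk falls with age, it hides part of a real effect. The information needed to avoid either outcome is already on the data collection list.

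**Working it through.** **No figure to reproduce.** The plan gives no number that bears on age coding. Its sample size is a recruitment figure: 12 sites × 170 = 2,040, against about 2,000.

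**Inputs from the documents.** N = 2,000 (section 4). Hospitalisation 53/907 = 5.8% (section 6.1). The 41% HIV share in the early report (section 2) is used here only as an assumed share of PLWHIV.

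**Assumptions, not in the documents.** Normal age distributions with the means and SDs below. The age effect is either log-linear (odds ratio 1.3 or 1.5 per decade) or a halving of the odds of the outcome from age 48. The true HIV odds ratio is 1.00. There is no vaccination or comorbidity term.

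**Step 1: why the top band matters.** Take PrEP users with mean 36, PLWHIV 5 years older, and SD 9 in both. Mean age inside the over-40 band is then 47.7 against 46.1, a gap of 1.6 years. At 1.5 per decade the spurious odds ratio within that band is exp(0.16 × ln 1.5) = exp(0.065) = 1.07. With PLWHIV 8 years older the means are 49.0 and 46.1, giving exp(0.29 × ln 1.5) = exp(0.118) = 1.12. Fitting all three bands together gives 1.05 and 1.10.

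**Step 2: fitted HIV odds ratio with the planned bands** (large-sample logistic regression, truth 1.00):

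| Mean age (SD), PLWHIV vs PrEP | 1.3 per decade | 1.5 per decade | Risk halves from 48 |
|---|---|---|---|
| 40 (10) vs 37 (9) | 1.03 | 1.05 | 0.97 |
| 42 (10) vs 36 (9) | 1.05 | 1.08 | 0.95 |
| 44 (11) vs 35 (9) | 1.08 | 1.14 | 0.93 |

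A 1:1 split changes no entry by more than 0.01. With identical age distributions the bias is zero. A 4-knot restricted cubic spline returns 0.99 to 1.00 throughout. A linear term returns 1.00 when the effect is linear and recovers most, not all, of a step.

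In a wider grid (SD 9, age odds ratio 1.2 to 2.0 per decade) the banded result is 1.01 to 1.05 for a 3-year gap, 1.02 to 1.10 for 5 years and 1.04 to 1.19 for 8 years. It reaches 1.30 only with an 8-year gap, SD 11 in PLWHIV and 2.0 per decade.

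**Step 3: what the bands already achieve.** In the 42-versus-36 case at 1.5 per decade the odds ratio with no age term is 1.28. The share removed on the log scale is 1 − ln 1.08/ln 1.28 = 1 − 0.077/0.247 = 69%.

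**Step 4: size against precision.** With 820 PLWHIV and 1,180 PrEP users at 5.8%, events are 47.6 and 68.4. The unadjusted SE is √(1/47.6 + 1/772.4 + 1/68.4 + 1/1,111.6) = 0.194, or about 0.20 once age is in the model. Then:

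- ln 1.05/0.20 = 0.24 SE
- ln 1.08/0.20 = 0.38 SE
- ln 1.14/0.20 = 0.66 SE
- ln 0.93/0.20 = −0.36 SE

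A shift of 0.66 SE raises the two-sided 5% error rate to P(Z > 1.30) + P(Z < −2.62) = 0.097 + 0.004 = 10%. A shift of 0.24 SE raises it to P(Z > 1.72) + P(Z < −2.20) = 0.043 + 0.014 = 5.7%. At the 13% hospitalisation of the early report the unadjusted SE is √(1/106.6 + 1/713.4 + 1/153.4 + 1/1,026.6) = 0.135, and an odds ratio of 1.14 would be ln 1.14/0.135 = 0.97 SE.

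**The case against.** **The bias is conditional.** It needs an age difference within bands and an age effect on the outcome, and the documents establish neither. This stands: the bands can leave confounding, and nothing shows that they will.

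**The Background does not show a severity step.** Section 1 describes the end of smallpox vaccination as "likely leaving the population below 40 to 50 years of age (depending on the country) more susceptible to mpox". A reader might infer that severity changes inside the over-40 band and that the protocol says so. It does not. The sentence concerns susceptibility to infection, and every participant already has PCR-confirmed mpox. The step at 48 above is an assumption, not a reading of section 1.

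**Vaccination and comorbidities are adjusted for.** They may absorb part of an age effect, so the figures above, which omit both, lean towards the high side. This stands in part. Section 6.2 collects "Orthopoxvirus vaccination history (if available", section 7.7 excludes variables with more than 20% missing, and a yes/no code does not separate childhood from outbreak vaccination. The documents give no missingness rate, so one cannot say that the variable will be lost either.

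**The effect is small against the precision.** An SE of 0.20 means a 95% interval of exp(1.96 × 0.20) = 1.48-fold either way, in a study that section 7.2 calls primarily descriptive. This stands for hospitalisation, and it sets the priority. It gives no reason to keep the bands when the alternative costs almost nothing.

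**Conclusion.** The point holds as a low-priority improvement. All adjusted PLWHIV-versus-PrEP models in 7.4 (first and second primary analyses) and 7.5 discard collected information on a confounder that the plan itself names. For age gaps of 3 to 9 years and an age odds ratio of 1.3 to 1.5 per decade, a null HIV effect would appear as 1.03 to 1.14. If risk halved from age 48 it would appear as 0.93 to 0.97. For hospitalisation at 5.8% that is at most about 0.7 SE. All of this rests on assumed ages and age effects, with no vaccination or comorbidity adjustment.

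Two wider readings are not supported. The first is that every primary model is affected: the third primary analysis, within PLWHIV, lists no age term and is outside this point, and the Fisher and Gray tests in 7.5 are unadjusted. The second is that better age coding would rescue the mortality hazard ratio. At 1 death in 907, about 2,000/907 = 2.2 deaths are expected, so that estimate is limited by events whatever the coding.

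**What to change.** In 7.4 and 7.5, replace the three bands in the adjusted PLWHIV-versus-PrEP models with continuous age derived from year of birth and date of diagnosis:

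- Use a restricted cubic spline with 4 knots where events allow, with knot positions fixed in advance as percentiles of the pooled age distribution.
- Use a linear term where events are sparse, as in small comorbidity subgroups, and state beforehand the number of events below which it applies.
- Carry age in the same form in the imputation model of 7.7.
- Keep the three bands for descriptive tables or as a sensitivity analysis.
- Do not justify the change by the susceptibility sentence in section 1.

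Cost: a change of wording and no new data. A 4-knot spline uses three parameters against two for the bands, and a linear term uses one. In the scenarios above the spline raises the SE of the HIV log odds ratio by about 5% at most. Fixing the form now also avoids a choice of age coding after the data are seen.
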